78 Notably, there is only one study that specifically explores the relationship between ankle joint
79 interventions, DKV, and anterior knee pain, and this study only examines the effects immediately
80 postintervention (31). More importantly, as mentioned earlier, most assessments focus on changes in
81 pain and biomechanics. To date, no studies have investigated the long-term effects of exercise
82 interventions on the structural changes in the hip, knee, and ankle soft tissues or explored the potential
83 mechanisms of recovery.

84 Telemedicine is a simple rehabilitation method that overcomes spatial limitations. Particularly
85 during the COVID-19 pandemic, to reduce the risk of face-to-face transmission, many patients were
86 unable to continue their rehabilitation at hospitals (38). As a result, telemedicine became an
87 alternative solution, allowing patients to continue their rehabilitation. Telemedicine not only
88 effectively reduces treatment costs but also improves patient adherence to treatment (39, 40).
89 Telehealth-delivered physical therapy, including telerehabilitation, has been shown in randomized

90 trials to be as effective as face-to-face care for musculoskeletal conditions—yielding comparable
91 improvements in pain, physical function, and quality of life—while systematic reviews report similar
92 outcomes across a broad range of conditions such as low back pain and knee osteoarthritis (41). These
93 findings demonstrate that physical therapy programs can be effectively and successfully administered
94 via telehealth in musculoskeletal populations (42, 43). Although some literature indicates that
95 telemedicine is effective in alleviating pain and improving knee function in anterior knee pain
96 patients, there is still a lack of high-level evidence to support this, and most studies have focused
97 solely on clinical symptoms (44). Therefore, this study adopted 8 weeks of telemedicine as an
98 intervention strategy to further understand the benefits of combining hip or ankle joint exercises on
99 exercise performance, clinical symptoms, and tissue structure in female patients with anterior knee
100 pain. We hypothesized that 8 weeks of telehealth-based supervised exercise, both the hip and ankle,
101 coupled with knee strengthening, would effectively improve DKV and pain in women with anterior
102 knee pain, and both groups would provide comparable benefits.

103

104 **Methods**

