131 anterior knee pain, and no changes in medication use were reported during the study.

132

133 Experimental Procedure and Random Grouping

134 A single-blinded randomized controlled trial was conducted, in which outcome assessors were
135 blinded to group allocation to reduce the risk of bias. Upon arrival at the research laboratory,
136 participants first performed a simple warm-up (5 minutes of cycling) before immediately undergoing
137 pre-tests. The measurements were conducted in the following order: pain index assessment, patellar
138 tendon stiffness measurement, ultrasound examination, ankle joint ROM measurement, DKV angle
139 measurement, and maximum muscle strength measurement. After completing the pre-test (T0),
140 participants randomly drew a numbered card from an opaque box to determine their group
141 assignment for the subsequent 8-week exercise intervention: Group A (ankle + knee joint exercise
142 group, AK), Group B (hip + knee joint exercise group, HK), or Group C (stretching group). After
143 grouping, participants were immediately instructed on and performed the assigned exercise
144 intervention once. Following three training sessions per week, post-tests (same as pre-tests) were
145 conducted at the 4th week (T1) and the 8th week (T2) (Figure 1). Throughout the exercise training
146 period, participants were guided and monitored by a professionally trained physical therapist.

147

148 Interventions

149 Participants in the hip + knee joint exercise group (HK group) and the ankle + knee joint exercise
150 group (AK group) received one-on-one exercise instruction from a physical therapist with a
151 background in sports medicine. The exercise training goals for the HK group included strengthening
152 the knee extensors (Figure 2(a) Primarily targets the quadriceps (knee extensors), improving knee
153 extension strength and stability 2(b) Also strengthens the quadriceps, with greater isolation of the
154 knee extensors compared to (a), focusing on controlled terminal knee extension 2(c) Works
155 the quadriceps, gluteal muscles, and to some extent the hamstrings, emphasizing closed-chain
156 strengthening and functional loading of the lower limb, while also training postural control), hip
157 external rotators (Figure 3(a) Strengthens the hip abductors (particularly gluteus medius) while
158 promoting pelvic stability during lateral movement 3(b) Activates the gluteus maximus and posterior

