237 weight-bearing activities, this study used a weight-bearing lunge test to measure the active
238 dorsiflexion angle of the ankle during weight-bearing. A measuring tape was placed on the floor, with
239 the participant's heel and second toe aligned with the tape. The participant started with their toes 10
240 cm from the wall, touching the wall with the knee while keeping the heel on the ground. The heel
241 must maintain contact with the floor. If the participant could easily touch the wall or could not reach it,
242 the distance was adjusted by 1 cm increments, gradually adjusting the distance forward or backward
243 according to the participant's ability until they could no longer keep the heel fully in contact with the
244 ground. At the maximum angle, a goniometer was used for measurement, with the fixed arm placed
245 flat on the ground and the movable arm aligned with the line connecting the lateral malleolus and the
246 head of the fibula. The test was repeated twice, and the average value was recorded (51).

247 Maximum Voluntary Isometric Strength: A handheld dynamometer (MicroFET3; Hoggan
248 Scientific LLC, USA) was used to measure the maximum isometric strength of the hip abductors,

249 knee extensors, ankle dorsiflexors, and ankle plantar flexors. Each test was repeated twice, and the
250 average value was recorded (52).

251

252 Statistics

253 The sample size for this experiment was estimated using G*Power and calculated using the priori
254 sample size for Repeated Measures ANOVA. The effect size (ES) was set at $f = 0.45$, with an alpha
255 value of 0.05 and a power of 80%. Based on the above calculations, the required sample size was 36
256 participants. Considering a potential 10% dropout rate, 40 eligible participants were to be recruited.
257 However, to increase the statistical power, the final target was to recruit 45 participants.

258 Data processing and analysis were conducted using SPSS 20.0 for Windows statistical software.
259 The significance level for all data was set at $p < 0.05$, and all numerical data were presented as mean
260 \pm standard deviation. The Shapiro–Wilk test was used to determine the normality of the data
261 distribution. If the data were normally distributed, a two-way ANOVA with repeated measures was
262 used to analyze the 3 group factors (hip + knee group, hip + ankle group, stretching group) \times 3 time

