263 factors (pre-test, week 4, post-test) to first examine the significance of the interaction effect. If the
264 interaction effect was significant, indicating that the group and testing time factors influenced each
265 other, a simple main effect test and Bonferroni post hoc comparisons were performed. A One-way
266 ANOVA analysis was used to compare intra-group differences before the intervention, followed by
267 Bonferroni post hoc comparisons. Training adherence was calculated using the formula: (actual

268 training sessions/24) * 100%. Test-retest reliability was verified using the Intraclass Correlation
269 Coefficient (ICC) to ensure the consistency of all measurements.

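### The DKV analysis uses pre-randomisation T0 as an outcome level, not a covariate, and describes arm comparisons only after a significant interaction, with no planned HK vs AK interval

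*Combined protocol and SAP*

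**What the plan says.** DKV is the primary outcome (Outcome measures) and is assessed at T0, week 4 (T1) and week 8 (T2). Experimental Procedure and Random Grouping places T0 before allocation: "After completing the pre-test (T0"), "participants randomly drew a numbered card from an opaque box to determine their group".

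The Statistics section says: "If the data were normally distributed, a two-way ANOVA with repeated measures was" the method, with three groups crossed with three time "factors (pre-test, week 4, post-test) to first examine the significance of the interaction effect". If that interaction is significant, "a simple main effect test and Bonferroni post hoc comparisons were performed". The only comparison outside this condition is a one-way ANOVA of pre-intervention values, which does not estimate a treatment effect.

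For reporting, "all numerical data were presented as mean" with standard deviation, at p < 0.05. No covariate, primary visit, arm pair or confidence interval for an arm difference is mentioned. The hypothesis, at the end of the Introduction, begins "We hypothesized that 8 weeks of telehealth-based supervised exercise, both the hip and ankle". It predicts that both programmes improve DKV and pain and do so comparably.

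**The concern.** A measurement taken before the card is drawn cannot respond to treatment. In a randomised comparison its natural use is as a covariate that removes between-person variation from the follow-up contrasts. Here it is one of three outcome levels. The within-subject interaction test does draw on T0, but the follow-up contrasts make no adjustment for it.

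The comparisons a reader will want are also conditional and unnamed. If the 4-df test is not significant, no post-randomisation arm contrast is described at all. If it is significant, HK vs AK is one of several generic Bonferroni comparisons, and a non-significant p-value could be taken as showing comparability. Only an interval can show how large a difference between the two programmes remains compatible with the data. With 15 women per arm, precision that costs no participants is worth having.

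**Working it through.** **Inputs from the documents.** Three arms of 15; three visits; alpha 0.05; power 80%; f = 0.45; N = 36, raised to 40 for 10% dropout and then to 45. The documents give no DKV standard deviation, time course or r, and do not say which effect f refers to ("sample size for Repeated Measures ANOVA. The effect size (ES) was set at" 0.45).

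**Reproducing N = 36** (noncentral F, 3 groups, 3 visits). Two routes reach it:
- Between-factors test, assumed correlation 0.5: lambda = 0.45² x 36 x 3/(1 + 2 x 0.5) = 10.9, df 2 and 33, power 0.814 (N = 33 gives 0.773).
- Interaction with the SPSS-type effect size: lambda = 0.45² x 33 x 2 = 13.4, df 4 and 66, power 0.818 (N = 33 gives 0.772).

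The dropout step gives 36/0.9 = 40.

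**Precision (free of any effect size).** Assume unit SD at each visit, equal correlation r between visits, and 15 per arm. Per-person variances are 1 for raw week 8, 2(1 - r) for change from T0 and 1 - r² for T0-adjusted. Adjustment also carries an expected factor of 1 + 1/40 for chance baseline imbalance. Therefore:
- adjusted/raw = 1.025(1 - r²)
- adjusted/change = 1.025(1 + r)/2

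For a raw contrast, the mean full width of the Bonferroni interval (three pairs) is 2 x 2.49 x sqrt(2/15) x 0.994 = 1.81 SD, where 0.994 is the mean of the pooled sample SD. The other widths scale by the square root of the variance ratio.

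| assumed r | 0.3 | 0.5 | 0.7 | 0.8 |
|---|---|---|---|---|
| adjusted/raw variance | 0.93 | 0.77 | 0.52 | 0.37 |
| adjusted/change variance | 0.67 | 0.77 | 0.87 | 0.92 |
| width, raw (SD) | 1.81 | 1.81 | 1.81 | 1.81 |
| width, change (SD) | 2.14 | 1.81 | 1.40 | 1.15 |
| width, adjusted (SD) | 1.75 | 1.59 | 1.31 | 1.10 |

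Break-even against raw is r = sqrt(1 - 1/1.025) = 0.16. Break-even against change is r = 2/1.025 - 1 = 0.95.

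**Power for one exercise arm vs control at week 8** (simulation, 40,000 trials per setting; both exercise arms equal; each contrast at 0.05/3). Gated means that the interaction must also be significant. Linear growth has half the effect at week 4; early onset has the full effect at both visits.

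| meaning given to f = 0.45 | analysis | r = 0.3 | 0.5 | 0.7 | 0.8 |
|---|---|---|---|---|---|
| week-8 means only, linear (d = 0.955) | gated raw | 0.34 | 0.42 | 0.51 | 0.55 |
| | gated change | 0.34 | 0.50 | 0.78 | 0.94 |
| | ungated adjusted | 0.58 | 0.69 | 0.86 | 0.96 |
| interaction, linear (d = 1.54/1.30/1.01/0.83) | gated raw | 0.88 | 0.80 | 0.57 | 0.40 |
| | gated change | 0.83 | 0.84 | 0.83 | 0.83 |
| | ungated adjusted | 0.97 | 0.94 | 0.90 | 0.88 |
| mean over visits, early (d = 1.43) | gated raw | 0.88 | 0.91 | 0.92 | 0.92 |
| | gated change | 0.79 | 0.92 | 0.99 | 1.00 |
| | ungated adjusted | 0.94 | 0.97 | 1.00 | 1.00 |

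The d values follow from f. For week-8 means only, d = 0.45/(sqrt(2)/3) = 0.955. For the interaction, lambda = 0.45² x 84 = 17.0 = 5d²/(1 - r). For means over three visits with T0 null, d = 0.955 x 3/2 = 1.43 (early) or 0.955 x 2 = 1.91 (linear). At d = 1.91, gated raw is 0.985 or more and gated change 0.966 or more, so the gain is at most about 3 points.

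**Error rates with no effect.** The interaction test rejects in about 5% of trials and each ungated adjusted contrast in 0.016-0.017. The three-pair family rate is 4-5%.

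**A case against relying on week 8.** If the effect is 0.955 SD at week 4 and halves by week 8, the 4-df test has power 0.48/0.64/0.88/0.98, against 0.25/0.30/0.42/0.57 for a 2-df adjusted test at week 8.

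**The case against.** The strongest reply is that testing the interaction first is standard and valid, and that on both routes that reproduce N = 36 it is well powered: with 45 women it has power 0.91 on the interaction route. On the between-factors route the contrasts gain little too. This stands, and it limits the point to the follow-up contrasts.

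Three stronger readings are tempting, and the documents do not support them.
- A reader might infer that the hypothesis requires three week-8 comparisons with week 8 as the primary visit. The Introduction mentions neither control nor a ranking of visits, and its 8 weeks describe the length of the programme. Making week 8 the only primary visit is a trade-off, as the fading-effect case shows.
- A reader might take the 24-41 point gain over gated raw contrasts at d = 0.955 as the trial's own planning case. That d matches neither route to N = 36.
- A reader might conclude that confidence intervals are excluded. Mean and SD is a descriptive format; intervals are unmentioned, not ruled out.

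Raw week-8 values are also the ordinary meaning of a simple main effect at a visit, so the change-score figures serve only as a second benchmark. Finally, much of the document is in the past tense, including medication use during the study, so replacing the analysis may no longer be open. None of this removes the case for adjusted, ungated contrasts with intervals, at least as a labelled supplement.

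**Conclusion.** The concern holds as an efficiency and specification weakness, not as an error in the planned test. The text is clear that T0 precedes allocation, is an outcome level, and is not a covariate, and that post-randomisation comparisons are conditional with no arm pair named.

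The size is conditional on r. Adjustment removes about 7-63% of contrast variance against raw week-8 values for r from 0.3 to 0.8, and 33-8% against change from T0. Below r of about 0.16 it is slightly worse than raw (2.5% more variance at r = 0). Power gains range from about zero to tens of points with the assumed effect and time course, and are small if f = 0.45 describes arm means averaged over visits. All of these figures assume equal correlations, complete data and 15 per arm.

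Adjustment will not by itself settle comparability. The HK vs AK interval would still be about 1.10-1.75 SD wide, and the documents state no margin.

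**What to change.** - Analyse DKV with T0 as a covariate, either in a mixed model with T1 and T2 as outcomes or by ANCOVA at week 8. The mixed model keeps week 4 in view.
- Report HK vs control, AK vs control and HK vs AK at week 8, and at week 4 if wanted, with Bonferroni-adjusted confidence intervals whether or not the interaction is significant. State how many comparisons the adjustment covers.
- Judge comparability from the HK vs AK interval, never from a non-significant p-value, and say plainly that it may be too wide to decide.
- Keep the group x time ANOVA for the time course.
- Reconcile the arm labels first: the Statistics section lists a hip + ankle group, whereas the arms are hip + knee and ankle + knee.

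The cost is revised wording, a different SPSS procedure and one error degree of freedom, with no new data or participants. If outcomes have already been seen, the planned ANOVA stays as the planned analysis, and the adjusted contrasts are dated and labelled supplementary or post hoc.

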Knee Strengthening With Hip vs. Ankle Exercises in Women With Patellofemoral Pain Syndrome

September 25, 2025

1 **Abstract**

2 **Purpose:** This study compared the effects of knee strengthening combined with either hip or ankle
3 joint exercises on dynamic knee valgus (DKV), visual analogue scale (VAS) scores during activity,
4 tendon stiffness, muscle structure, ankle range of motion, and muscle strength in women with anterior
5 knee pain. **Methods:** Forty-five female recreational athletes aged 20–40 with anterior knee pain were
6 randomly assigned to three groups: hip + knee exercises (HK group, n = 15), ankle + knee exercises
7 (AK group, n = 15), and stretching alone (control group, n = 15). The HK and AK groups received
8 supervised telehealth-based exercise sessions (30 minutes/day, 3 times/week for 8 weeks), while the
9 control group received only an educational pamphlet. Assessments were conducted at baseline, 4
10 weeks, and 8 weeks.

11

12 **Key Words:** (1) Dynamic alignment (2) Tele-rehabilitation (3) Pain modulation (4) Muscle strength.

13 **Introduction**

14 Anterior knee pain refers to clinical symptoms of pain around the patella that occur during
15 activities such as squatting, running, and climbing stairs due to increased pressure on the
16 patellofemoral joint. Anterior knee pain is a non-contact knee injury, typically characterized by a
17 gradual onset of pain around the knee joint that is not related to trauma. Additionally, the pain tends to
18 worsen with increased activity, leading to limitations in movement and reduced exercise performance
19 (1, 2). Statistics show that this condition accounts for 25-40% of all knee injuries, with a significantly
20 higher prevalence in women than in men (3). This may be related to anatomical differences,
21 particularly the larger knee valgus angle in women. Additionally, characteristics such as muscle
22 strength and muscle coordination in women may also contribute to greater knee joint instability,
23 further increasing the risk of anterior knee pain, impacting quality of life, and raising healthcare costs
24 (4-6).

25 Treating anterior knee pain is particularly challenging because multiple factors cause it. There is
26 currently no consensus on treatment strategies, but scholars generally agree that the primary causes of
27 anterior knee pain include increased dynamic knee valgus (DKV) angle, weakness in the knee and hip

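### With exactly three arms, Bonferroni on the arm pairs is valid but stricter than 5% family-wise error at a visit requires; a step-down test would recover some power at little cost

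*Combined protocol and SAP*

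**What the plan says.** The Statistics section sets a 3 × 3 repeated-measures ANOVA (three arms; baseline, week 4, week 8) and looks first at the interaction. If it is significant, "a simple main effect test and Bonferroni post hoc comparisons were performed". The section does not define the Bonferroni family. It does not say that a non-significant simple main effect stops the pairwise tests. DKV is the primary outcome, but no visit is named as primary. The significance level is 0.05 throughout, with no stated family-wise limit across visits or outcomes.

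The last paragraph of the Introduction hypothesises that the hip and ankle programmes, each "coupled with knee strengthening, would effectively improve DKV and pain in women with anterior" knee pain, would also give comparable benefit. The Abstract gives 15 women per arm. The sample-size paragraph states that "the required sample size was 36", allows for 10% dropout, and ends with "the final target was to recruit 45 participants".

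**The concern.** Three arms give three pairwise equalities, and the number that are true can be 3, 1 or 0, never exactly 2, because two equalities imply the third. Plain Bonferroni ignores this and tests every pair at 0.05/3. If two arms are equal and the third differs, only one false claim is possible, yet that pair is still tested at 0.0167.

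The natural way to support the hypothesis is to show each programme better than control, which needs two of the three pairs to reach significance with 15 women per arm. A threshold stricter than necessary reduces the chance of showing both.

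**Working it through.** **1. The plan's own figure.** The inputs are f = 0.45, alpha 0.05, power 80%, three groups and three measurements. The documents give no between-visit correlation; ρ = 0.5 is assumed. For the between-groups test, λ = f²·N·m / (1 + (m − 1)ρ) = 0.2025 × 36 × 3 / 2 = 10.935. With 2 and 33 df, power is 81.4%, so N = 36 reproduces. Dropout: 36 / 0.90 = 40, as stated.

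**2. What f = 0.45 means in SD units.** If both programmes beat control by d and equal each other, the arm means are (d, d, 0). Their standard deviation is d√2/3, so d = 0.45 × 3/√2 = 0.955 at one visit. The range d = 0.8 to 1.2 used below brackets this.

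**3. Thresholds for the ordered p-values, three arm pairs at one visit.**

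| Method | Smallest | Middle | Largest |
|---|---|---|---|
| Bonferroni | 0.0167 | 0.0167 | 0.0167 |
| Holm | 0.0167 | 0.025 | 0.05 |
| Shaffer | 0.0167 | 0.05 | 0.05 |

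Holm and Shaffer stop if the smallest p fails. They never reject less than Bonferroni, because the first step is the same and no later threshold is lower.

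**4. Error at one visit.**
- All three arms equal: any false claim needs the smallest p below 0.05/3, so the error is at most 3 × 0.05/3 = 5%.
- Two arms equal: one true equality, tested at 0.05 at most, so the error is at most 5%. Bonferroni uses 0.05/3 = 1.7% here.

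No F test enters this argument.

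**5. Power through the plan's sequence.** Simulation of the interaction test followed by the week-8 pairs: 15 per arm, normal data, 40,000 runs per scenario, half the week-8 effect at week 4, no stop at the simple main effect. Power to show both programmes better than control at d = 0.955:

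| ρ | Bonferroni | Holm | Shaffer | Gain, Holm | Gain, Shaffer |
|---|---|---|---|---|---|
| 0.3 | 26.4% | 29.7% | 34.2% | 3.3 | 7.8 |
| 0.5 | 31.1% | 35.7% | 41.8% | 4.6 | 10.7 |
| 0.7 | 37.3% | 43.2% | 51.6% | 5.9 | 14.3 |

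Over d = 0.8 to 1.2 and ρ = 0.3 to 0.7 the gains are about 2 to 6 points (Holm) and 6 to 14 points (Shaffer).

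**6. Error in an adverse case.** Arms equal at week 4, both programmes better by 2 SD at week 8, so the interaction is almost always significant:

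| Method for the pairs | Week 4 | Weeks 4 and 8 together |
|---|---|---|
| Bonferroni | about 4.2–4.4% | about 5.5–6% |
| Holm or Shaffer | about 4.2–4.4% | about 8–9% |
| Unadjusted, three-arm F as hard stop | about 5% | about 9–10% |
| Unadjusted, no hard stop | about 12% | about 15–17% |

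Step-down costs nothing at week 4, where all arms are equal. The higher total across the two visits comes from week 8, where the one true equality is tested at up to 0.05 instead of 0.0167.

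**The case against.** Bonferroni is conventional and controls the error at each visit. Replacing it is a gain in efficiency, not a correction. That stands.

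A reader might go further and infer that the plan already requires a significant three-arm test at each visit, so that Bonferroni is a second penalty that adds no protection and costs 16 to 19 points of power. The documents do not support this, for three reasons.

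- **The gate.** The only stated condition is the interaction, which has 4 df and is not a three-arm test at a visit. The simple main effect test is listed beside the pairwise comparisons, not as a stop before them.
- **The protection.** Bonferroni does protect. It lowers the error when two arms are equal (1.7% against up to 5%). In the adverse case it holds week-4 error near 4.3%, where unadjusted pairs without a hard stop reach about 12%. It also lowers the total across weeks 4 and 8.
- **The size.** The 16 to 19 points belong to one visit, a three-arm F gate alone, and unadjusted pairs. At d = 0.955 power is 58.1% against 39.4% (18.7 points). With f = 0.45 read in SDs of the three-visit average, d = 0.955/√(2/3) = 1.169 and the gap is 16.2 points. At d = 1.2 it is already 15 points (82% against 67%). Through the interaction gate, F-gated unadjusted pairs gain about 7 to 17 points, depending on a correlation that the documents do not give.

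Two further objections stand. The plan never states that both programmes must beat control; that criterion is inferred from the hypothesis. And the document is dated September 2025 and describes parts of the conduct in the past tense, so relaxing a threshold after results are known would look opportunistic.

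**Conclusion.** The point holds as a cheap improvement. Bonferroni is valid here, but more conservative than needed to hold 5% at a visit with exactly three arms. The gain from step-down is about 6 to 14 points with Shaffer and 2 to 6 with Holm, for showing both programmes better than control at week 8.

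That per-visit error stays within 5% follows from the logic of three groups and needs no assumed effect. The size of the gain rests on assumptions outside the documents: equal effects of 0.8 to 1.2 SD, half the effect at week 4, a correlation of 0.3 to 0.7, a Bonferroni family of the three arm pairs at one visit, and joint success of both programmes. Total error across weeks 4 and 8 rises to about 8 to 9% in the adverse case. The plan sets no limit across visits, and Bonferroni over three arm pairs does not hold 5% there either (about 5.5 to 6%).

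The three visit pairs within an arm were not examined. They are repeated measures, and the result should not be carried over to them.

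**What to change.** In the Statistics section, replace the Bonferroni wording for the arm pairs with, for example: *At each visit the three between-arm comparisons are tested by Shaffer's step-down procedure: the smallest p-value is multiplied by 3; if it is below 0.05, the other two are each tested at 0.05; otherwise testing stops. The primary comparison is DKV at week 8.* Holm (multipliers 3, 2, 1) is the more familiar choice, with a smaller gain. Unadjusted pairs at 0.05 are acceptable only if the three-arm test at that visit is written as a hard stop. For visit pairs within an arm, keep Bonferroni or go no further than Holm.

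The change takes one or two sentences and no new data; the adjustment can be done by hand from unadjusted p-values. There are two costs. Bonferroni simultaneous confidence intervals will no longer match the tests exactly. The incidental protection across visits also falls; naming week 8 as the single primary visit deals with this for the main claim. If the results have already been seen, report the Bonferroni analysis as planned and label the step-down results as post hoc.
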